3.2 OVERVIEW OF STUDY DESIGN

This is a prospective, multi-center, double-blinded, randomized, placebo-controlled, phase-II clinical trial. The total sample size required is 294 subjects with ICH. Subjects will be randomized in a 1:1 ratio to receive either DFO at 32 mg/kg/day (up to a maximum daily dose of 6000 mg/day), or a matching saline vehicle (placebo), given by IV infusion for 3 consecutive days, in a blinded manner. Treatment will be initiated within 24 hours after ICH symptom onset. Subjects will undergo repeated clinical, imaging, and laboratory evaluations at regular intervals throughout their participation in the study, from the day of randomization until day 180. All adverse events will be assessed until day-7 or discharge (whichever is earlier), and new SAEs until day-90. Mortality and continuing SAEs will be assessed until day 180. Functional status will be determined by mRS scores, in person at 30 ± 7 and 90 ± 7 days; the patients or their surrogates will be contacted by phone on days 60 ± 7 and 180 ± 7 to assess mRS [Merino, 2005].

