8 STATISTICAL CONSIDERATIONS

8.1 RANDOMIZATION PROCEDURES

A combination of minimization and biased coin methodologies will be used to randomize participants to either DFO or placebo [Pocock 1975; Taves 1974]. The minimization method aims to control imbalance in the treatment groups with respect to pre-specified baseline characteristics; the biased coin approach is adopted to avoid deterministic assignment. Throughout the trial, the probability of treatment assignment will take into account the imbalance associated

with clinical site, baseline ICH score, OTT, baseline ICH volume, baseline NIHSS score, and concurrent use of anticoagulants at the time of ICH onset.

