8.2 STUDY ENDPOINTS AND DATA ANALYSIS

8.2.1 CLINICAL ENDPOINTS

The primary efficacy outcome measure is the mRS, dichotomized to define good functional outcome as mRS score of 0-2 at 90 days. At the conclusion of the study, the proportion of DFO-treated subjects with a good outcome will be compared to the placebo proportion in a futility analysis. The primary futility hypothesis is tested via generalized linear model relating the probability of a good outcome to the treatment. Adjustment for OTT, ICH score, baseline ICH volume, NIHSS score, and anticoagulant use are included in the model to obtain proper significance due to the inclusion of these variables in the randomization scheme. The binomial distribution for Y , with the identity link, is used to derive an estimate of the adjusted risk difference for good outcome. The primary futility hypothesis, $H_0: (\pi_{DFO} - \pi_{placebo}) \geq 0.12$, will be tested at one-sided alpha (the probability that an effective intervention will be called ineffective, or futile) 0.10. The corresponding alternative hypothesis, $H_A: (\pi_{DFO} - \pi_{placebo}) < 0.12$, defines futility as a treatment effect less than absolute 12% in favor of DFO. The futility analysis will be conducted using a one-sided 90% upper confidence bound on the risk difference, which is consistent with the one-sided alternative hypothesis and stated level of significance. To declare futility, the entire interval must lie below the value 0.12, indicating that the true difference in risk of good outcome is less than 0.12 with 90% confidence. Under this design, a significant result would suggest that it would be futile to move DFO forward to Phase III testing.

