All adverse events or complications will be submitted electronically via the WebDCU™ system and assigned to a system-organ class and preferred term using MedDRA coding dictionary. The number and percent of all adverse events will be summarized for each treatment arm by event type. Tables will be generated to detect any clinically significant laboratory abnormalities in change of values from baseline to end of the last infusion. We anticipate no missing safety data regarding adverse events, since patients will remain hospitalized and closely monitored until day-7 or discharge (whichever is earlier). The cumulative incidences of each AEOSI, as well as mortality, will be compared via 95% confidence intervals. Mortality will also be assessed via the log rank test for comparing survival curves.

Analysis of the safety data regarding the occurrence of ARDS will be carried out continuously throughout the trial by the unblinded study statistician, who will notify the EC and DSMB if recruitment must be stopped. The DSMB will be notified of each individual ARDS occurrence upon confirmation by the MSMs, per their request. Analysis of other safety data by the DSMB will occur semiannually (or more frequently if requested by the DSMB). If any of these analyses reveal serious emerging concerns, the EC, in consultation with the DSMB, may implement modifications to assure safety as necessary. Apparent, consistent and persistent evidence of net harm that tends to overwhelm any benefit may allow for premature termination of the study.

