8.4 SAMPLE SIZE CALCULATION

The sample size is calculated to achieve 80% power for the futility analysis described above using a one-sided alpha level of 0.10. It is anticipated that approximately 28% of control subjects will have mRS 0-2 at 3 months; this is based on the weighted average of the good outcome proportions reported in the placebo-treated subjects of the Factor VII, FAST, GAIN, and CHANT trials [Haley 2005; Lyden 2007; Mayer 2005-2008]. If the true good outcome proportions in the DFO and placebo arms are identical ($\pi_{tx}=0.28$, $\pi_{ctrl}=0.28$, a truly futile situation), 254 subjects (127 in each arm) are required to test the futility hypothesis with 80% power. This calculation takes into account the 0.12 null value specified in the futility hypothesis [Chow, 2003]. The primary analysis will be conducted according to a modified Intent-to-Treat (ITT) principle, wherein subjects in whom the study drug infusion is not initiated will be excluded from the analysis. Therefore, the final sample size was inflated by a factor of 1.11 (Friedman, Furberg, and DeMets) to account for dilution of the treatment effect associated with a conservative drop-out rate of 5% (due to loss-to-follow-up (LTFU) and

withdrawal of consent), and an additional factor of 1.04 to account for randomized subjects in whom the study drug is not initiated. Therefore, the final sample size is 294 subjects.

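### The mortality comparison in 8.2.2 names no adjustment for the minimisation factors that 8.2.1 adjusts for, so it is conservative to the extent that those factors predict death

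*Protocol*

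**What the plan says.** Section 8.1 describes the allocation: "A combination of minimization and biased coin methodologies will be used to randomize participants to either DFO or placebo". The assignment probability responds to differences between the arms that have to do "with clinical site, baseline ICH score, OTT, baseline ICH volume, baseline NIHSS score, and concurrent use of anticoagulants at the time of ICH onset". The biased-coin probability is not given.

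Section 8.2.1 adjusts the primary futility model for OTT, ICH score, ICH volume, NIHSS and anticoagulant use (not site). The reason it gives is that these variables "are included in the model to obtain proper significance due to the inclusion of these variables in the randomization scheme".

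Section 8.2.2 has two sentences on the mortality comparison. The first is "The cumulative incidences of each AEOSI, as well as mortality, will be compared via 95% confidence intervals". The second is "Mortality will also be assessed via the log rank test for comparing survival curves". Neither names a covariate, a stratum, a significance level or a decision rule.

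Mortality appears in the second primary objective (section 1.1), in the secondary objectives at 90 and 180 days (section 1.2), and among the safety endpoints of particular interest through day 180 (section 8.2.2).

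**The concern.** The reason that 8.2.1 gives for adjusting concerns how patients were allocated. It does not depend on the endpoint, so it carries over to any between-arm comparison of an outcome that the factors predict. Minimisation makes the arms more alike on those factors than chance would. An unadjusted log-rank variance still assumes chance-level imbalance, so it is too large and the test rejects too seldom under no effect. Separately, leaving out prognostic covariates weakens a survival comparison under any allocation scheme.

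In an efficacy test, conservatism protects patients. In a comparison meant to reveal harm, it makes a real excess of deaths easier to miss. The preceding trial of this drug, HI-DEF, was terminated on safety grounds (section 2.2.3), so the mortality result will be read closely.

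**Working it through.** **Reproducing the plan's own figure.** The protocol gives no size, power or death count for the mortality test, so its sample size is the only figure to reproduce. The 8.4 inputs are 28% good outcome in both arms, margin 0.12, "one-sided alpha level of 0.10" and 80% power:

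n per arm = (1.2816 + 0.8416)² × 2 × 0.28 × 0.72 / 0.12² = 4.508 × 0.4032 / 0.0144 = 126.2, so 127 per arm and 254 in all.

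254 × 1.11 × 1.04 = 293.2, so 294. This agrees with 8.4. Removing the 1.04 factor for infusions never started gives 294 / 1.04 ≈ 282 treated subjects, the safety sample.

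**Expected deaths.** The documents give 7% mortality in HI-DEF (section 2.2.3) and 15% at 90 days in Phase I (section 2.2.2). 282 × 0.07 ≈ 20 and 282 × 0.15 ≈ 42 deaths. Follow-up here runs to day 180, so these rates are assumptions. Section 2.1.1 gives about 40% at one month for ICH in general, taken here as an upper bound for this selected population.

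**Simulation.** 282 subjects, 1:1, Pocock-Simon minimisation on the five clinical factors plus 25 sites, with a biased coin of 0.8 (assumed). Deaths were followed to day 180. The two tests were an unadjusted log-rank test at |z| > 1.96 and a Cox model with treatment and the five clinical factors. The joint discrimination of the factors for death (AUC) is an assumption. Each setting used 4,000–6,000 runs under no effect and 2,500–3,000 runs at a hazard ratio of 2 given the covariates. Monte Carlo error is about 0.3 points for size and 1 point for power.

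| Mortality | AUC | Size, log-rank | Size, Cox | Power at HR 2, log-rank | Power at HR 2, Cox |
|---|---|---|---|---|---|
| 7% | 0.73 | 4.5% | 4.5% | 40% | 42% |
| 7% | 0.74 | 4.8% | 4.6% | 42% | 43% |
| 7% | 0.84 | 3.6% | 5.1% | 33% | 38% |
| 7% | 0.87 | 3.3% | 5.1% | 29% | 40% |
| 15% | 0.74 | 3.7% | 5.1% | 66% | 73% |
| 15% | 0.75 | 4.1% | 5.2% | 67% | 72% |
| 15% | 0.82 | 2.5% | 4.8% | 56% | 73% |
| 15% | 0.84 | 3.2% | 5.1% | 53% | 67% |
| 15% | 0.87 | 2.1% | 5.1% | 41% | 70% |

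**Check on the size column.** If the log-rank z has standard deviation s under no effect, the true size is 2Φ(−1.96/s). The simulated s was 0.975 (7%, AUC 0.73), 0.948 (15%, AUC 0.74) and 0.840 (15%, AUC 0.87). These give 4.5%, 3.9% and 2.0%, against 4.5%, 3.7% and 2.1% counted directly.

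**Sensitivity.**
- At 15% mortality and AUC 0.82, a coin of 0.7, 0.8 or 0.95 gives log-rank size 3.9%, 2.5% or 2.4%.
- At 25% mortality, size is 3.0–4.0% (AUC 0.75) and 0.9% (AUC 0.88).
- At 40% mortality, size is 2.6% (AUC 0.76) and 1.1% (AUC 0.86).

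**Where the power goes.** At AUC 0.87, unadjusted power at 7%, 15% and 25% mortality was 33%, 43% and 49% under simple randomisation, and 29%, 41% and 49% under minimisation. Minimisation therefore accounts for at most about 4 points. The rest of the gap to the adjusted test (40%, 70% and 87%) comes from leaving out the covariates.

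**Behaviour of the remedies.** The adjusted Cox test kept its size at 4.4–6.1%, except for 7.9% at 7% mortality with AUC 0.92. Six coefficients on 20 to 42 deaths means only about 3 to 7 deaths per coefficient. In a separate minimisation simulation at 7–15% mortality, a log-rank test stratified on three binary prognostic factors had size 4.2–5.3% and about 1–10 points more power at HR 2 than the unadjusted test.

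**The case against.** The strongest reply is that the protocol names a log-rank test without calling it unstratified, and that details of a supplementary safety test usually go in the statistical analysis plan, which is not at hand. The adjustment sentence in 8.2.1 is written for the primary futility model only. The log-rank test is an addition to the confidence intervals, with no alpha or decision rule attached. The DSMB reviews deaths with no limit on the number of analyses (section 10.4), and the only formal safety rule concerns ARDS (section 7.7).

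Much of this stands. A later document could add strata, and no stopping decision depends on this test. It does not remove the point: the protocol chose to name both the mortality method and the reason for adjusting, and applied that reason to one endpoint only. The confidence intervals beside the log-rank test name no adjustment either.

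Three stronger readings are tempting, and the documents do not support them.
- A reader might infer that the safety test runs far below 5%. With moderate predictors at 7–15% mortality it runs at 3.7–4.8%. Lower values need stronger predictors or higher mortality.
- A reader might blame the power loss on minimisation. The simple-randomisation comparison shows otherwise.
- A reader might take the minimisation factors to be the strongest predictors of death. The protocol does not say so. Section 3.3 names hematoma growth as a major predictor, and growth is not a minimisation factor.

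**Conclusion.** The inconsistency and its direction hold. Log-rank size was below 5% in every minimised setting, and unadjusted power was below adjusted power in every setting. The magnitude is open. At 7–15% mortality the true size is about 4–5% with moderate predictors (AUC about 0.74) and about 2–4% with strong ones (AUC 0.82–0.87). The power loss at HR 2 runs from about 1 to about 30 points.

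These figures rest on assumed mortality, prognostic strength and coin probability, so confidence in the magnitude is moderate. Undue width of the 95% intervals would follow by the same mechanism if they use an unadjusted variance, but it was not quantified. This is a free improvement to the mortality analysis and does not show that the planned one is invalid.

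**What to change.** In 8.2.2, and in the statistical analysis plan:
- Make the main mortality comparison a Cox model with treatment and the factors already used in 8.2.1: OTT, ICH score, ICH volume, NIHSS and anticoagulant use. The alternative is a log-rank test stratified on a few main prognostic categories.
- Keep the model parsimonious, because only about 20–40 deaths may be available. Use simple codings and avoid cross-classifying all five factors as strata. State in advance which terms are dropped if deaths are few.
- Report covariate-adjusted mortality risk differences at 90 and 180 days with 95% confidence intervals.
- Keep the unadjusted survival curves and log-rank test as description.

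The cost is a short change to 8.2.2 and the matching analysis code. All five factors are already used for randomisation, so no patients, visits or measurements are added.

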8.3 STUDY SAMPLES

ALL analyses will involve data from two samples:

1- Modified Intent-to-Treat (mITT): Outcome data from all subjects who are randomized and in whom the study infusion begins, even if it is discontinued prematurely, will be analyzed. Classically, ITT analysis is used in Phase III trials and includes all subjects randomized, regardless of whether they receive the treatment or not. However, in order to evaluate the efficacy of DFO as administered, randomized subjects in whom the study infusion is never initiated will be excluded from the primary analysis. As a sensitivity analysis, the futility hypothesis will also be assessed according to the ITT principle. All subjects randomized will be included and considered in the treatment group to which he/she was randomized, regardless of the treatment actually received. The outcomes for subjects in whom treatment is never initiated will be imputed based on available baseline data.

Safety analysis will involve data from all patients in whom study infusion begins, even if it is discontinued prematurely (i.e. the mITT sample).

2- Per-protocol sample, i.e. all subjects who have at least one post-treatment assessment and no major protocol violations that affect the analysis. The Executive Committee (EC) will adjudicate major protocol violations and patients' inclusion in the per-protocol population before unblinding. Analyses based on the per-protocol sample will be supportive in nature.

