4.1 Inclusion Criteria

- 1) Age ≥ 18 and ≤ 80 years
- 2) The diagnosis of ICH is confirmed by brain CT scan
- 3) NIHSS score ≥ 6 and GCS >6 upon presentation.
- 4) The first dose of the study drug is expected to be administered within 24h of ICH symptom onset (as described above).
- 5) Functional independence prior to ICH, defined as pre-ICH mRS ≤ 1 .
- 6) Signed and dated informed consent is obtained.

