4.3.4 ENROLLMENT

Clinically and radiologically eligible patients for whom informed consent is obtained (from the subject or a legal representative or family member) will be randomized. Calculation of the ICH score [Hemphill 2001; please refer to appendix III] is required prior to randomization. Administration of the study drug to eligible candidates will only be permitted after completion of liver function tests and urine analysis, if not done upon presentation.

Participants should be reassessed immediately prior to the study drug administration to obtain a pre-treatment GCS and baseline NIHSS. Patients who exhibit significant clinical and neurological deterioration (i.e. develop fixed and dilated pupils or GCS decreases to ≤ 6) prior to administration of the first dose of the study drug should not receive the study drug, and their participation in the study should be terminated.

To ensure that all eligible subjects presenting within 12h of ICH onset are enrolled in a timely fashion without delay: 1) enrollment and time from door (arrival-to-emergency room)-to-infusion will be monitored on an ongoing basis, and every attempt will be made to ensure that subjects are treated as soon as possible from symptom-onset; and 2) if enrollment into the early (≤ 12 h) window is disproportionately low, we will implement a strategy of forced recruitment whereby each site will be required to enroll one subject into the early time window for each subject enrolled into the later ($>12-24$ h) window (or maintain its overall ratio of ≤ 12 h to $>12-24$ h to at least 1:1) before subsequent enrollment into the later time window is permitted at this site.

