6.1.1 CLINICAL AND LABORATORY ASSESSMENTS

The following assessments will be carried out throughout the 90-day study period:

Upon screening of potential study subjects: 1) Review of head CT and determination of the time of ICH onset or the time the patient was last known to be without presenting deficits; 2) Demographic data; 3) Medical history; 4) Review of medications; 5) General physical examination; 6) Neurological examination, including NIHSS and GCS; 7) Visual and auditory assessment (which includes assessments for cataracts, visual loss or field cut, disturbed color vision, hearing loss, and presence of tinnitus), whenever possible in awake patients; 8) Determination of pre-morbid mRS; 9) Review of admission laboratory tests - Hematology [hemoglobin, hematocrit, red blood cell count and platelet count]; Coagulation [partial thromboplastin time and international normalized ratio]; and serum albumin; and 10) Review of all inclusion/exclusion criteria. A baseline chest x-ray is required to rule out the presence of bilateral pulmonary infiltrates or pulmonary edema. A pregnancy test is required for all women of childbearing potential prior to enrollment into the study. Subjects in whom all eligibility criteria are met should be considered for enrollment, and those who agree to participate via signed and dated informed consent should be enrolled.

Participants should be reassessed immediately prior to the study drug administration to obtain a pre-treatment baseline. **The Pre-treatment baseline reassessments include:** 1) Vital signs, including blood pressure and heart rate; 2)

Neurological examination, including NIHSS and GCS to confirm stability of their neurological status and to obtain pre-treatment baseline scores; and 3) Assessment for new adverse events since screening. Patients who exhibit significant clinical or neurological deterioration (i.e. develop fixed dilated pupils or GCS decreases to ≤ 6) prior to administration of the first dose of the study drug should not receive the study drug, and their participation will be terminated.

Administration of the study drug should only be permitted after obtaining pre-treatment blood sample for serum chemistry and glucose, hepatic function tests, and urine analysis (if not already done upon arrival to the ED).

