Subjects who receive the study drug(s) will be evaluated daily for the first 3 days (during study drug infusion while in hospital) and on day-7 or discharge from the hospital, whichever occurs first. Clinic visits will take place on days 30 ± 7 and 90 ± 7 . Telephone interviews will be conducted on day 60 ± 7 and 180 ± 7 .

The following assessments should be performed **after each daily infusion** (every 24 ± 6 h) and through the day following completion of the last infusion: 1) General physical examination; 2) Visual and auditory assessments; 3) Neurological examination, including NIHSS and GCS; and 4) Vital signs, including blood pressure and heart rate. A repeat head CT scan and blood samples for hematology, serum chemistry, renal and hepatic function tests, coagulation studies, and urine analysis should be obtained within 24 ± 6 h following the last infusion of the study drug. Vital signs (blood pressure and pulse) and neurological functions should be assessed at least once every 4h during intravenous drug infusions. Daily urinary output checks should be carried out every day until the day following the last infusion. In addition, the following data must be checked at least once daily for all intubated patients (or more frequently in patients with changes in respiratory status requiring changes in ventilator settings and increased oxygen requirement) throughout day-7 or discharge and entered into Web-DCU™: 1) $\text{PaO}_2/\text{FiO}_2$ ratio; 2) Plateau and peak pressures; and 3) Chest X-ray results (when available). **A chest x-ray is required if the $\text{PaO}_2/\text{FiO}_2$ ratio is < 300 .**

On day-7 or Discharge (whichever comes first), the following assessments are done: mRS, NIHSS, GCS, MoCA and visual and auditory assessments.

During hospitalization, the NIHSS and GCS should be done any time a subject's neurological status deteriorates, or whenever the investigator believes it is prudent to do an assessment. Laboratory assessments beyond those required for the study should be done whenever clinically indicated.

The **Day-30 (± 7)** will be an in-person visit comprised of a general physical examination, visual and auditory assessments, review of SAEs, and assessments of NIHSS, SIS-16, MoCA and mRS.

The **Day-60 (± 7)** assessments, which will be completed via telephone, will be comprised of a functional assessment to obtain a score on mRS and query for SAEs.

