7.4 CRITERIA FOR INTERVENTION DISCONTINUATION

The investigators may terminate the study drug infusion if, in their judgment, its continued administration poses harm to the patient's medical condition. The only pre-established criteria for premature discontinuation of the study drug are: 1) severe allergic reaction or anaphylaxis; 2) worsening of renal functions, defined as serum creatinine >2 mg/dl on 2 repeated measures 8 hours apart; 3) development of ARDS based on Berlin criteria/definition (see appendix VII); or 4) if the patient or his proxy voluntarily withdraws consent. Subjects whose study drug is discontinued but who do not withdraw consent should still be followed for 180 days.

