8.5 LOSS-TO-FOLLOW-UP AND MISSING DATA

Extensive efforts will be made to keep missing data, particularly the primary outcome (mRS at 90 days), to a minimum, and to ensure near complete follow-up. Missing primary outcome data will be imputed via standard multiple imputation (MI) methods (i.e. via logistic regression model predicting outcome based on pertinent baseline and treatment data). As a sensitivity assessment, we will use the Last Observation Carried Forward (LOCF) approach, wherein the last available score will be carried forward for missing day 90 assessments. If the treatment effect is robust, we expect to reach similar conclusions via these imputation methods, particularly for minimal missing data (<5%).

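### The ITT sensitivity analysis imputes a day-90 mRS for randomised subjects who are never dosed, although one telephone or proxy contact could supply it (minor, cheap improvement)

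*Protocol*

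**What the plan says.** - **Order of events.** Under Section 4.3.4, consented eligible patients are randomised and then reassessed just before dosing. Those who develop fixed dilated pupils or a GCS of 6 or less "should not receive the study drug, and their participation in the study should be terminated". Section 6.1.1 repeats the rule: "should not receive the study drug, and their participation will be terminated".
- **Who is followed.** The visit schedule in Section 6.1.1 is written for dosed subjects: "Subjects who receive the study drug(s) will be evaluated daily for the first 3 days". Section 7.4 keeps early stoppers in follow-up: "Subjects whose study drug is discontinued but who do not withdraw consent should still be followed for 180 days". Neither covers a subject whose infusion never began.
- **How they are analysed.** Section 8.3 excludes never-started subjects from the primary mITT analysis and offers ITT as a sensitivity analysis of the futility hypothesis. For that analysis, "The outcomes for subjects in whom treatment is never initiated will be imputed based on available baseline data". The general rule for missing day-90 data in Section 8.5 is multiple imputation "via logistic regression model predicting outcome based on pertinent baseline and treatment data".
- **What is already allowed.** Section 6.1.1 permits a telephone mRS at day 90 case by case, and a proxy report when the subject cannot answer. Section 8.5 aims for near-complete follow-up of this outcome.

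**The concern.** The ITT analysis is the plan's own check on leaving never-started subjects out of the primary analysis. For these subjects the check rests on a model, because the protocol stops collecting their data. A later statistical analysis plan can choose the model but cannot recover outcomes that were never collected.

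The loss is also selective: deteriorators leave because they got much worse. Section 4.1 requires "GCS >6 upon presentation", and the pre-dose rule bars dosing at 6 or below, so no subject dosed per protocol has a GCS in the range that defines many of them. A model fitted to dosed subjects must extrapolate in GCS. At stake is how far the ITT result can be read as an independent check, not the primary result.

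**Working it through.** **1. The plan's sample size.** Section 8.4 gives one-sided alpha 0.10, power 80%, 28% good outcome in both arms and a margin of 0.12.

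n per arm = 2 × 0.28 × 0.72 × (1.2816 + 0.8416)² / 0.12² = 126.2, so 127 per arm and 254 in total, as stated. The drop-out factor is 1/(1 − 0.05)² = 1.108, about 1.11. Then 254 × 1.11 × 1.04 = 293.2, which becomes 294 when rounded up to an even total.

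**2. How many subjects are concerned.** The 1.04 factor implies 294 − 294/1.04 = 11.3 never-started subjects for all reasons, about 3.8% of those randomised. The protocol does not give the deteriorators' share, so I take 3, 6 and 12, with 12 as the ceiling.

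**3. Set-up.**
- 141 dosed subjects per arm; placebo good outcome 0.28; true difference 0, 0.05 or 0.12.
- Deteriorators fall in either arm with probability 0.5.
- Futility is declared if RD + 1.2816 × SE < 0.12. This is unadjusted, whereas the plan's model is adjusted.
- Assumptions not in the protocol: deteriorators' true good-outcome rate 0-5%; imputed rate 2-12%.
- Observed-outcome results are exact. Imputed results come from 100,000 simulated trials per setting, with 40 imputations at a fixed rate combined by Rubin's rules.

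**4. Primary analysis.** mITT declares futility in 83.5%, 49.8% and 9.6% of trials at true differences of 0, 0.05 and 0.12. These subjects do not enter it, so nothing here changes it.

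**5. Imputed against observed ITT.** This comparison measures what imputation costs.

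| Deteriorators | Trials in which the two ITT decisions differ |
|---|---|
| 3 | about 0.1-1.5% |
| 6 | about 0.1-2.2% |
| 12 (ceiling) | about 0.2-3.2% |

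The low ends come from 0% true and 2% imputed good outcome. The high ends come from 5% true and 12% imputed, at a true difference of 0.05, where the decision is close to even.

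**6. Direction.** Never-dosed subjects cannot gain from the drug, so including them dilutes the difference. With k deteriorators, the expected difference at a true 0.12 is 0.12 × 141/(141 + k/2).

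| k | Diluted difference | Futility declared by observed ITT at a true 0.12 (mITT 9.6%) |
|---|---|---|
| 3 | 0.1187 | 10.4% |
| 6 | 0.1175 | 10.8% |
| 12 | 0.1151 | 11.6% |

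Observed outcomes add 0.8, 1.2 and 2.0 points to 9.6%. Imputation at an assumed 8% good outcome adds about 0.7, 1.0 and 1.6, so most of the dilution comes with any realistic ITT analysis.

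**The case against.** **The design is coherent and disclosed.** Sections 4.3.4, 8.3 and 8.4 fit together: no drug, exclusion from the primary analysis, imputation in a sensitivity analysis, and an allowance in the sample size. Section 8.3 gives its reason, which is to evaluate the drug as administered. Section 7.4 concerns a different group that is in the primary analysis, so it does not contradict Section 4.3.4. All of this stands. The point is a better choice, not a contradiction.

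**Imputation may do most of the work.** A reader might infer that the model would use screening values only, borrow outcomes from subjects stable enough to be dosed, and hand back the mITT answer. The protocol does not support that as the natural reading. Section 4.3.4 calls the pre-dose NIHSS baseline, Section 6.1.1 has the reassessment done "to confirm stability of their neurological status and to obtain pre-treatment baseline scores", and Table 6.2 marks NIHSS and GCS in its baseline column. The worsened scores therefore belong to the available baseline data. NIHSS has no upper entry limit, so severe dosed subjects can inform the model through it. What remains is the extrapolation in GCS.

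**A larger number is tempting.** Observed ITT reverses the mITT decision in 1.3-5.4% of trials over the same scenarios. That is the sensitivity analysis doing its job and does not measure harm from imputing.

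**A rule could replace follow-up.** Scoring deteriorators as mRS 3-6 would match observed outcomes in every trial if none did well. At 5% good outcome it would differ in 0.3-0.7% (3), 0.6-1.4% (6) or 1.1-2.4% (12) of trials. This is a fair alternative for a later plan, but it leaves the actual outcomes unverified and does not suit subjects never started for other reasons.

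**Conclusion.** The point holds as a minor improvement to consider. The protocol ends data collection for randomised subjects who deteriorate before dosing, has no day-90 mRS for any never-started subject, and so must impute outcomes that its own telephone and proxy routes could supply.

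The cost of imputing is a different ITT futility decision in about 0.1-3.2% of trials across all scenarios, in a supportive analysis of at most about 4% of subjects. That range rests on the assumed number of deteriorators, the assumed good-outcome rates and an unadjusted bound.

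A reader might go further and infer that the primary result is biased. The protocol does not support that: the loss occurs before any study drug is given and under blinding, and the mITT analysis does not use these outcomes. Nor does the point make ITT the better estimate, since it dilutes the difference toward futility.

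**What to change.** Leave the no-drug rule, the mITT primary analysis and N = 294 unchanged.

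1. In Sections 4.3.4 and 6.1.1, replace termination of participation with wording such as: *no study drug; vital status and mRS collected at day 90 (telephone or proxy allowed) unless consent is withdrawn*. Apply the same day-90 contact to every randomised subject whose infusion never starts, whatever the reason. Day 180 is not needed, because the ITT sensitivity analysis concerns the day-90 futility hypothesis.
2. In Section 8.3, use these observed outcomes in the ITT sensitivity analysis. Keep imputation from baseline data, naming the pre-dose NIHSS and GCS, for any never-started subject whose day-90 mRS is still missing, so that nobody is left without a rule.
3. In Section 8.3, state that ITT dilutes the difference toward futility and should be read with that in mind.

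The cost is a few sentences of wording and one telephone or proxy contact for about 12 subjects. The downside is the dilution shown above: at a true difference of 0.12, the ITT analysis declares futility in 10.4-11.6% of trials, against 9.6% for mITT.
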